### 8.1 Inclusion /Exclusion criteria

Inclusion Criteria	Exclusion criteria

 
• Men aged 16 years and over.
 
• Men who present to their GP with a complaint of one or more bothersome lower urinary tract symptoms#
 
• Men able and willing to give informed consent for participation in study
 
• Men able and willing to undergo all index tests and reference test, and complete study documentation.
 
 
# This would include men on current treatment, but who are still symptomatic
	
 
• Men with neurological disease or injury affecting lower urinary tract function
 
• Men with LUTS considered secondary to current or past invasive treatment or radiotherapy for pelvic disease Men with other contraindications to urodynamics e.g. Heart valve or joint replacement surgery within the last 3 months, immunocompromised/immunosuppressed.
 
• Men with indwelling urinary catheters or who carry out intermittent self-catheterisation
 
• Men whose initial assessment suggests that clinical findings are suggestive of possible:               
 
○ prostate or bladder cancer*
 
○ recurrent or persistent symptomatic UTI**
 
○ renal impairment
 
○ retention
 
 
 
• Men unable to consent in English or Welsh where a suitable translator is not available. This is a multi-centre study based in primary care, and we cannot guarantee translation facilities at all sites
 
 
*According to standard NHS cancer pathways. If later deemed unlikely, then eligible for study participation.
 
**If UTI successfully treated but LUTS remain, then eligible for study.

	
>This is a multi-centre study based in primary care, and we cannot guarantee translation facilities at all sites.

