#### **14.4 Referral Rates**

We will ascertain the number of men recommended for referral by GPs who used the output of the prediction model and considered the management options recommended and compare this with 5-year data from the Clinical Practice Research Datalink (CPRD; historical control) to estimate potential impact of the aid on referral rates. The CPRD holds anonymised primary care records from almost 700 practices across the UK and by July 2013 had abstracted data from primary care records stored by a variety of bespoke GP systems for almost 12 million patients with median follow-up of 5.1 years and [9]. The CPRD has previously been used to define cohorts of men with benign prostatic hypertrophy for epidemiological studies [10, 11]. We will use the CPRD to estimate recent trends in referral rates for men presenting to UK primary care with an incident episode of LUTS. For these historical control data, our denominator will consist of men aged 16 and over whose primary care records contain a Read code indicating an incident presentation with LUTS. We will define incident presentations as those without a prescription for an alpha-blocker (except doxazosin), 5-alpha reductase inhibitor or combination drug at the time of incident presentation and without a LUTS related Read code in the preceding 365 days. Where doxazosin is prescribed, we will only include men who have a Read code for hypertension and no prior record of LUTS. To include only probable benign cases, we will exclude men with a Read code suggesting a urological malignancy, haematuria, urinary tract infection or a prostate specific antigen above the age-specific reference range within 28 days after incident LUTS presentation. Our numerator will consist of men from our denominator whose primary care records contain a Read code indicating referral to specialist urology services within 28 days of the incident LUTS presentation. This short time period is to increase likelihood that referral is due to initial presentation and not to treatment failure. We will describe referral rates over time and by age-group and compare these with the referral rate occurring during practice participation in the PriMUS study to understand the potential impact of widespread use of the aid on secondary care services. We will specify the assumption that this referral rate reflects decisions based on the reference standard urodynamic result, and will model variations on this according to the observed accuracy of the decision aid in the validation study.

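### Section 14.4 sets referral in screened study men against a CPRD control that omits most section 8.1 exclusions, so the contrast is confounded by case mix of unestablished sign

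*Protocol*

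**What the plan says.** Protocol section 14.4 defines the control in detail. The denominator is men aged 16 and over with an incident LUTS Read code, not on most LUTS drugs at that time and "without a LUTS related Read code in the preceding 365 days". Then, with the stated aim "To include only probable benign cases", it removes men with a code suggesting "urological malignancy, haematuria, urinary tract infection or a prostate specific antigen above the age-specific reference range within 28 days after incident LUTS presentation". The numerator is men from that denominator with "a Read code indicating referral to specialist urology services within 28 days of the incident LUTS presentation".

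The study side is the men in the study whom their GPs refer (section 5.2). They have passed section 8.1, which bars eight clinical categories:

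- neurological disease affecting the lower urinary tract;
- "Men with LUTS considered secondary to current or past invasive treatment or radiotherapy for pelvic disease";
- other contraindications to urodynamics;
- indwelling catheter or self-catheterisation;
- findings suggesting prostate or bladder cancer;
- recurrent or persistent symptomatic UTI;
- renal impairment;
- retention.

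A footnote there softens the UTI bar: "If UTI successfully treated but LUTS remain, then eligible for study". A ninth criterion concerns language.

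Sections 14.4 and 17.4.1 present the difference between the two rates as the potential impact of the aid. Section 14.4 adds one caveat, that the study rate reflects the urodynamic result. It gives none on case mix.

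**The concern.** A historical control is informative only if its men resemble those it is compared with. Here one group was screened by a GP against eight clinical categories and the other was filtered by a short code list that covers two of them. A man found to be in retention at presentation and referred the same day counts in the CPRD denominator and numerator, but could not have entered the study. The same holds for renal impairment found at the first assessment. In the other direction, a man whose UTI was treated but whose LUTS persist can be in the study, while his UTI code can remove him from CPRD.

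The percentage change in referral is a listed secondary outcome (section 5.4), and section 4 calls referral rate an important outcome of interest. Part of any difference between the two rates may come from who is counted, not from what the GP was told.

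**Working it through.** No sample size or power figure rests on this point, so there is no plan figure to reproduce. There are three checks.

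**1. Exclusions set side by side.**

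| Section 8.1 category | In the CPRD rule? |
|---|---|
| Neurological disease | No |
| LUTS secondary to pelvic treatment | No |
| Contraindications to urodynamics | No |
| Catheter or self-catheterisation | No |
| Possible prostate or bladder cancer | Yes, through malignancy and PSA codes |
| Recurrent or persistent UTI | Yes, but broader than in the study |
| Renal impairment | No |
| Retention | No |

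Two of eight are addressed and six of eight (75%) are not. CPRD also removes haematuria, which section 8.1 does not name.

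**2. The time window.** The only look-back is 365 days, for LUTS codes. The 28-day phrase can be read in two ways:

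- If it covers all four items, a malignancy coded before presentation does not remove a man.
- If it covers only the PSA, the other codes have no window, and a UTI or haematuria code at any time removes him.

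Neither reading brings in the six missing categories, and neither matches the study's UTI rule.

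**3. Possible size.** Let R be the observed control rate, q the share of control men whom the study would bar, and b their 28-day referral rate. Since R = (1 - q) x r + q x b, the rate among study-eligible men is r = (R - q x b) / (1 - q). The bias in the control is R - r; a positive value means the control is too high.

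R = 30% is the 2013 CPRD proportion in section 4. The documents give neither q nor b, so both are assumptions. Entries are r, with the bias in percentage points in brackets.

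| q | b = 0% | b = 10% | b = 30% | b = 50% | b = 70% | b = 90% |
|---|---|---|---|---|---|---|
| 5% | 31.6 (-1.6) | 31.1 (-1.1) | 30.0 (0) | 28.9 (+1.1) | 27.9 (+2.1) | 26.8 (+3.2) |
| 10% | 33.3 (-3.3) | 32.2 (-2.2) | 30.0 (0) | 27.8 (+2.2) | 25.6 (+4.4) | 23.3 (+6.7) |
| 15% | 35.3 (-5.3) | 33.5 (-3.5) | 30.0 (0) | 26.5 (+3.5) | 22.9 (+7.1) | 19.4 (+10.6) |

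Example: q = 15%, b = 90% gives (0.30 - 0.135) / 0.85 = 0.194. The bias is positive only when b exceeds the overall rate.

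The UTI mismatch follows the same logic. If men with a UTI code are a share u of the aligned control and are referred at rate v, the aligned rate is 0.30 x (1 - u) + u x v. With u = 10% and v = 5% this is 0.270 + 0.005 = 27.5%, so the present rule is 2.5 points too high. With v = 30% there is no effect, and above 30% the sign reverses. Both u and v are assumptions.

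**The case against.** Five arguments stand against the point.

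- **The rule aims at benign cases, not study-eligible ones.** This is right as a reading of the stated purpose. Retention, catheter use and neurological disease are not malignancy, so keeping such men does not break that purpose. But the rate is then compared with that of men who were screened for these conditions, and the mismatch remains.
- **The sign is open.** A reader might infer that the rule must inflate the control rate, so that the aid would show a fall in referral even if it changed nothing. The documents do not support this. Men with known neurological disease or catheters may already be under specialist care and generate no new referral. Other features of the comparison could raise the study rate: section 8.1 admits men on treatment who are still symptomatic, whereas CPRD removes men on most LUTS drugs; and study referrals are ascertained at about 3-6 months (section 11.3), against 28 days in CPRD. This objection stands in full.
- **Some examples go too far.** Section 8.1 does not name a past cancer diagnosis as such, and it bars pelvic treatment only when the LUTS are considered secondary to it. A code suggesting malignancy may also catch some suspected-cancer records. These cases should not carry the point; retention and renal impairment do.
- **The study rate might be practice-wide.** Sections 14.4 and 17.4.1 speak of referral during practice participation. But section 5.2 counts men in the study, and both sections tie the rate to urodynamic results, which the study provides only for participants.
- **Code lists belong in the analysis plan.** Detailed lists do. Here, however, the protocol itself fixes which conditions are excluded and the only window, so an analysis plan that followed it would carry the mismatch forward.

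**Conclusion.** The point holds as a case-mix mismatch. The CPRD denominator omits six of the eight clinical exclusions that every study man has passed, looks back only for LUTS codes, handles UTI differently, and leaves the scope of the 28-day window unclear. The referral contrast is therefore confounded.

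An upward bias in the control is probable where retention, renal impairment or suspected cancer prompts referral, but it is not shown. At a 30% control rate, with 5-15% of control men barred and 0-90% of them referred, the bias runs from about -5 to +11 points and is zero if barred men are referred at the same 30%. The 30% is itself only a stand-in: section 4 does not say that it was obtained under the section 14.4 rule, and the proportion it reports moved from 10% to 30% between 2009 and 2013.

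The primary outcome, diagnostic accuracy, is untouched. This is an inexpensive improvement to one secondary outcome.

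**What to change.** In section 14.4:

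1. Apply the codable section 8.1 exclusions to the CPRD denominator, using codes up to and including the day of presentation. For retention, renal impairment and suspected cancer, also use codes up to 28 days after.
2. State which of the listed codes the 28-day window covers.
3. Align the UTI rule with section 8.1, so that men whose UTI was treated but whose LUTS remain stay in the control.
4. State that exclusions needing clinical judgement can only be approximated by codes. These are LUTS attributed to pelvic treatment and cancer that is later judged unlikely.
5. Report the control referral rate with and without these exclusions. The gap between the two rates then shows the sign and size of this part of the bias.

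The cost is extra Read-code lists, one rewritten paragraph and a somewhat smaller control cohort. No new data source or participants are needed. The differences in current treatment and in length of ascertainment remain after this change and should be stated as limits of the comparison.

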### **5.4 Secondary Outcome Measures**

- Construction of a patient management algorithm to guide initial treatment for men with LUTS
- Construction of a prototype online decision aid for use in primary care
- Qualitative analysis of patients and clinicians views on the use of a LUTS decision aid in the primary care setting
- Percentage change in referral rates to secondary care for men with LUTS

- Estimation of costs / savings of implementation of the primary care LUTS decision aid both from a population and individual patient perspective.

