## **Results**

Results from the uroflowmetry and urodynamics will be compiled and fed back to the GP via secure fax or email where the GP will be responsible for following up the patient as appropriate. Guidance on further management and treatment decisions will be provided to GPs, but the clinical management of the patient is at the discretion of their treating clinician.

The participants' NHS medical notes will be reviewed at approximately 3-6 months post assessment to record the clinical management and treatment decisions.

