### **11.3 Follow-up**

The participants will be followed up at approximately 3-6 months after their second visit (following the urodynamics reference test). Follow up will ascertain the management decisions that have been made by the GP after considering results and recommendations from the index and reference tests.

As a minimum requirement, we will collect the decisions regarding medical treatment and referral rates. We will also collect information regarding any study specific adverse events that have been experienced, as well as ensuring that all serious adverse events have been captured and reported.

A review of medical notes will be done by the research nurses to establish and report decisions in relation to advice and recommendations given to the patient regarding things like lifestyle changes.

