## **17.4 Other Analyses**

### **17.4.1 Referral rates**

The potential impact of the decision aid on referral rates will be calculated by expressing the difference between rates occurring during GP practice participation in the PriMUS study including consideration of urodynamic diagnoses provided by use of the reference test with the historical control of practices participating in the CPRD data collection.

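### The referral-rate comparison counts CPRD referrals by Read code within 28 days but sets no code or 28-day condition for study participants, so its two numerators are not like for like

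*Protocol*

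**What the plan says.** Section 5.4 lists "Percentage change in referral rates to secondary care for men with LUTS" as a secondary outcome. Section 17.4.1 obtains it by "expressing the difference between rates occurring during GP practice participation in the PriMUS study" and the CPRD historical control.

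The control numerator is specified in section 14.4: "Our numerator will consist of men from our denominator whose primary care records contain a Read code indicating referral to specialist urology services". The code must appear "within 28 days of the incident LUTS presentation". The section explains that the short window is meant to pick up referral prompted by the first presentation rather than by failed treatment.

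The study numerator has no matching specification. Section 14.4 speaks of men for whom the GP recommended referral, while the objective in section 5.2 speaks of men actually referred. Section 11.3 says "As a minimum requirement, we will collect the decisions regarding medical treatment and referral rates" but names no source. The Results part of section 11 says that participants' "NHS medical notes will be reviewed at approximately 3-6 months post assessment to record the clinical management and treatment decisions". Section 11.3 also says "A review of medical notes will be done by the research nurses to establish and report decisions", but that sentence goes on to advice and recommendations such as lifestyle changes, not referral.

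The only adjustment stated for the comparison, in section 14.4, concerns the fact that study referrals reflect urodynamic results. It will be varied by the observed accuracy of the decision aid. Coding completeness is not mentioned.

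**The concern.** A difference or percentage change between two rates is interpretable only if the event is counted in the same way on both sides. Here the control counts a coded entry. The study side can count a recommendation, or a referral visible in a letter or free text, whether or not a code was entered. It can also count events later than 28 days, which the control rule excludes by design.

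Someone reading a full set of notes will usually find at least what the codes show. If the notes show more, the fuller count sits on the study side only. That pushes the apparent change upward, against the reduction in referrals that the study hopes to see: section 4.1 discusses the saving if referrals were halved. Matching calendar years and populations would not remove this.

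**Working it through.** **1. The two numerators side by side**

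| | CPRD control (14.4) | Study participants (11, 11.3, 14.4) |
|---|---|---|
| Event | Referral to specialist urology | Referral recommended by the GP (14.4); men referred (5.2) |
| Evidence required | Read code in the primary care record | No code condition; follow-up and notes review is the natural reading |
| Window | 28 days from incident presentation | No window stated for the count; notes reviewed at about 3-6 months after assessment |
| Alignment or adjustment for ascertainment | None stated | None stated |

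**2. Is there a figure to reproduce?** No. The protocol gives no expected percentage change, no power and no coding completeness for this comparison. What follows is a sensitivity calculation on assumed values.

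**3. Formula.** Let p be the true referral rate on each side and s the fraction of true referrals that the counting rule captures.

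Apparent change = (s_study × p_study) / (s_CPRD × p_control) - 1

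With no true change (p_study = p_control) and complete study capture (s_study = 1), this reduces to 1/s_CPRD - 1, whatever the base rate. With a true halving it is 0.5/s_CPRD - 1.

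**4. Results.** Assumed s_CPRD runs from 1.00 to 0.70; assumed s_study is 1.00 or 0.95.

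| s_CPRD | No true change, s_study = 1.00 | No true change, s_study = 0.95 | True halving, s_study = 1.00 |
|---|---|---|---|
| 1.00 | 0% | -5.0% | -50.0% |
| 0.95 | +5.3% | 0% | -47.4% |
| 0.90 | +11.1% | +5.6% | -44.4% |
| 0.80 | +25.0% | +18.75% | -37.5% |
| 0.70 | +42.9% | +35.7% | -28.6% |

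For example, at s_CPRD = 0.80: 1/0.80 - 1 = +25.0%; 0.95/0.80 - 1 = +18.75%; 0.5/0.80 - 1 = -37.5%.

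**5. Check on the fix.** If one rule is applied to both sides and coding is equally complete on both, s_study = s_CPRD and the term cancels: no true change reads 0% and a true halving reads -50%.

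**6. What the table leaves out.** It covers coding only. The longer study-side look-back and the counting of recommendations rather than referrals would be expected to add events on the study side too, but the protocol gives nothing from which to size them.

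**The case against.** The strongest reply is that the protocol leaves the study-side count open rather than fixing it wrongly, and that a code list and counting rule normally belong in the statistical analysis plan, which is not shown. That has some force. But the protocol fixes one numerator down to code and window, describes the other as a recommendation, and sets the two rates against each other. Someone following that text would compare unlike events.

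Four stronger readings are tempting, and the document does not support them.

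- A reader might infer that nurses' notes review is the stated source of the referral count. It is the likely source, but no sentence says so, and the nurse sentence in 11.3 concerns advice such as lifestyle changes.
- A reader might infer that the comparison is biased by construction. Bias from coding arises only if codes miss referrals that the notes reveal. If capture is equal the bias is zero. If CPRD coding is complete and the study misses 5%, the sign reverses (-5.0%). Section 12.1 lets men withdraw from notes review, so complete study capture is not assured.
- A reader might take the 30% in section 4 as a true rate and compute what the control would read. That 30% is itself attributed to CPRD, so it cannot serve as the truth against which CPRD coding is judged. The ratios above do not need it.
- A reader might infer that the cost work inherits the problem. Section 17.3 describes a simple cost comparison and does not name the referral change as an input. The saving from halved referrals in 4.1 is background.

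It is also fair to say that this is a secondary outcome, intended to estimate potential impact against a historical control. The primary outcome, diagnostic accuracy, is untouched.

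**Conclusion.** The point holds as a mismatch of definition and ascertainment: coded referral within 28 days on one side, and recommended or notes-based referral without a code or 28-day condition on the other, with nothing in 14.4 or 17.4.1 to align them. The likely direction is to raise the study rate relative to the control and so understate a reduction. That direction depends on the study side capturing more than the codes do. The size is unknown. Under complete study capture and assumed code sensitivities of 1.0, 0.95 and 0.8, unchanged referral would read as 0%, +5% and +25%. These are illustrations, not estimates. The matter deserves correction because the change is cheap and the outcome is a named one, but it does not bear on the study's main conclusion.

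**What to change.** In 14.4 and 17.4.1, define the study-side numerator for the CPRD comparison by the same urology-referral Read code list and the same 28-day rule, taken from participants' coded practice records. State the index date from which the 28 days run. This needs a deliberate choice, because section 9.1 admits men who presented up to 6 months before the practice search, so a window counted from presentation could close before study results reach the GP.

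Report the notes-based or recommended-referral count separately, as descriptive.

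Optionally, use participants who have both sources to estimate code sensitivity, and show the control rate divided by that estimate. This should be a sensitivity analysis only, with the stated assumption that coding is similar in CPRD practices and years and is not altered by taking part in the study.

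The cost is a few sentences and a small coded-record extract, made when the notes are reviewed as already planned. Practices already run Read-code searches for recruitment. The headline study rate may come out lower than the notes-based one. The change does not settle the separate difference in population: 14.4 restricts the control to incident presentations without listed LUTS drug treatment, whereas section 8.1 also admits men who are still symptomatic on treatment.

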## **9 Recruitment, Screening and Registration**

### **9.1 Participant identification**

Potential participants will be recruited from primary care practices across the three network hubs. Recruitment strategies may differ between hubs depending on local geographic and organisational factors.

Participating practices will conduct a search of their patient electronic records using 'pre-defined read codes' to identify all potentially eligible patients who have presented within the last 6 month(s) at the start of the study and at least three additional times throughout the duration of the study. These patients will be 'flagged' in their general practice clinical record using pre-specified read codes in order to allow easy identification of patients, when they contact the surgery, who could be eligible to participate.

Practices will have the option to send relevant patients a letter informing them about the study (on practice headed paper) and a Patient Information Summary Leaflet, and invite the patient to attend the practice for a consultation.

Study posters, leaflets and adverts using electronic visual aids (where appropriate) will be used in practice waiting areas to inform patients about the study.

Participating clinicians will also be asked to approach eligible patients opportunistically during routine practice sessions.

Upon presentation, the PriMUS study will be introduced and the patient information pack (including the Patient Information Sheet, Patient Information Summary Leaflet, Consent Form, Urodynamics Leaflet and Frequency Volume Chart) provided to the patient during their primary care consultation for a complaint of lower urinary tract symptoms.

The GP will have the option to consent a patient to enter the study during the initial consultation visit, if the patient meets the eligibility criteria and they feel this is appropriate. If the patient is not consented during the initial GP Consultation, those who express interest will complete the Consent to Contact Form, which will be passed to the local research nurse. The patient will be contacted by telephone ideally within a week by a research nurse based at the local research network hub, and invited to attend a study appointment.

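### The referral outcome compares incident, untreated CPRD men counted to 28 days with a broader study cohort whose referral count has no stated cut-off

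*Protocol*

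**What the plan says.** Section 5.4 lists as a secondary outcome "Percentage change in referral rates to secondary care for men with LUTS". Section 14.4 defines the CPRD comparator in detail. The denominator is men with an incident LUTS presentation, without a listed LUTS drug at that time (doxazosin has its own rule) and without a LUTS code in the preceding year. The numerator is men with "a Read code indicating referral to specialist urology services within 28 days of the incident LUTS presentation", and the protocol gives its reason: "This short time period is to increase likelihood that referral is due to initial presentation and not to treatment failure".

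The study side is wider. Section 8.1 says of the men who may join: "This would include men on current treatment, but who are still symptomatic". Section 9.1 has practices search their records to "identify all potentially eligible patients who have presented within the last 6 month(s) at the start of the study". Section 11.3 says: "The participants will be followed up at approximately 3-6 months after their second visit", and referral is collected then; no time limit for counting a referral is given.

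Section 14.4 opens by counting "the number of men recommended for referral by GPs who used the output of the prediction model". The same section ends by assuming that the study referral rate reflects decisions based on urodynamics, and section 17.4.1 describes the study rate as "including consideration of urodynamic diagnoses provided by use of the reference test".

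**The concern.** A difference between two rates estimates an effect only if the rates would agree when nothing has changed. Here they need not, for two reasons. The CPRD rate excludes men on listed treatment and men with a recent LUTS code, whereas the study rate may include both. The CPRD numerator is cut at 28 days specifically to keep out referrals after treatment failure, whereas the study numerator has no such limit and its data source extends several months further.

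The result could therefore show a change in referral with no real change behind it, or mask a real one. Section 4 calls referral rate an important outcome of interest, so the figure is likely to be read as evidence of service impact. There is also a labelling problem. The opening of 14.4 credits GPs who used the model, but section 6.1 builds the model from the first cohort's data, so the care of those men cannot have been guided by it.

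**Working it through.** The protocol gives no target effect, sample size or power for this comparison, so there is no planned figure to reproduce. The definitions compare as follows.

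| Element | CPRD rate (14.4) | Study rate |
|---|---|---|
| Previous presentation | No LUTS code in 365 days | May have presented up to 6 months earlier (9.1) |
| Treatment | No listed LUTS drug, special rule for doxazosin | Treated, still symptomatic men eligible (8.1) |
| Clock starts | Incident presentation | Not stated; review is timed from the urodynamics visit (11.3) |
| Count ends | 28 days | Not stated; review at about 3-6 months (11, Results; 11.3) |

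Section 14.4 also plans description by calendar time and age group, and modelling of variations according to the aid's accuracy. None of these aligns the window or the case mix.

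**Window, illustration only.** Let p be the 28-day referral proportion, with hazard h = -ln(1-p)/28 per day. After day 28 let the hazard be f·h. The proportion referred by day T is R(T) = 1 - exp{-h[28 + f(T-28)]}, and the apparent change with no true effect is R(T)/p - 1. For a true halving, h is recomputed from p/2 and R(T) is still divided by p. Section 4 gives 30% referred in 2013 without stating a window; using it as p is an assumption, and f is an assumption throughout.

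For p = 0.30, h = 0.3567/28 = 0.01274. With f = 0.05 and T = 90, R = 1 - exp(-0.01274 × 31.1) = 0.327, and 0.327/0.30 - 1 = +9%. The others follow in the same way:

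| f | No effect, day 90 | No effect, day 180 | True halving, day 90 | True halving, day 180 |
|---|---|---|---|---|
| 0.05 | 32.7%, +9% | 36.5%, +22% | -45% | -38% |
| 0.10 | 35.3%, +18% | 42.3%, +41% | -40% | -26% |
| 0.25 | 42.5%, +42% | 56.9%, +90% | -26% | +6% |

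Starting from p = 0.10 (the 2009 figure in section 4), the no-effect distortion for the same f is +10%, +21% and +51% at day 90, and +25%, +50% and +120% at day 180. If f = 0, or both sides use 28 days, the distortion is zero and a true halving shows as -50%.

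**Case mix, illustration only.** If a share s of study men are not incident and are referred k times as often as incident men, the apparent change is (1-s) + s·k - 1. With s = 0.4 (assumed), k = 0.5 gives -20% and k = 1.5 gives +20%. Multiplying by an assumed window inflation w:

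- k = 0.5, w = 1.1: 0.8 × 1.1 - 1 = -12%
- k = 0.5, w = 1.3: 0.8 × 1.3 - 1 = +4%
- k = 1.5, w = 1.1: 1.2 × 1.1 - 1 = +32%
- k = 1.5, w = 1.3: 1.2 × 1.3 - 1 = +56%

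So the window alone acts in one direction, but the net sign depends on quantities that the documents do not give.

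**Sampling error for scale.** At 30% and n = 675, the 95% half-width is 1.96 × √(0.3 × 0.7/675) = 3.5 percentage points. Moving from 30% to 35.3% already exceeds that.

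**The case against.** The strongest reply is that the 3-6 months is when the notes are read, not a counting window. Section 11.3 records decisions made by the GP after considering the results, so a count of first decisions fits the text, and an SAP might fix it. That stands: a reader might infer that the study numerator includes every referral up to the review, treatment failures among them, but the protocol does not say so. What remains is that no window is stated, while the CPRD side is fixed at 28 days and the two rates are compared directly. The population mismatch does not depend on this reading.

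Other objections also limit the point:

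- A reader might take the 30% in section 4 as the 28-day rate. That section names no window, so percentages built on it are illustrative.
- A reader might infer that early referrals have been selected out of the men found by record search. Section 8.1 does not exclude men already referred, and 9.1 also recruits at the presenting consultation. Depletion is plausible but not stated.
- The choice of CPRD year is largely covered, because 14.4 plans to describe rates over time and by age group.
- The end of 14.4 and section 17.4.1 already attribute the study rate to urodynamics, so only the opening of 14.4 needs correcting.
- The saving of about £1.3 million in section 4.1 comes from a hypothetical halving applied to CPRD rates and does not rest on this outcome.

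**Conclusion.** The concern holds as a problem of comparability. The study and CPRD populations differ as written, and no common window is set. If all referrals found at review are counted, the window difference can only raise the study rate and conceal a reduction. Case mix can push either way, so the net direction is unknown. The size cannot be derived from the documents. The illustration (no-effect changes of +9% to +90% from the window, and ±20% from case mix) rests on the assumed p, f, s and k, and shows only that the bias could exceed sampling error. The outcome is secondary and presented as an estimate of potential impact against historical controls. The primary sensitivity and specificity results are unaffected.

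**What to change.** 1. **Population.** Use the medical and medication history taken at registration (9.4), together with the notes, to flag study men who meet the CPRD incident definition. Make the main referral comparison in them, and report treated or previously presenting men separately.
2. **Window.** At the planned notes review, record the dates of presentation, of results sent to the GP and of referral. Count study referrals within a fixed window whose start and length are both stated, and add a CPRD numerator of the same length beside the 28-day one. Report separately any study referral made before results reached the GP, since a clock running from presentation alone would mix these in.
3. **Attribution.** Reword the opening of 14.4 so that the observed contrast is attributed to urodynamic results supplied to the GP, in line with the end of 14.4 and with 17.4.1. Keep the aid's effect to the modelled scenario.

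The cost is protocol or SAP wording, one more CPRD extraction window and three dates per man. The downsides are a smaller study denominator for this outcome and, with a longer window, some treatment-failure referrals on both sides. Keeping the 28-day CPRD figure alongside makes that visible.
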